9.6 Analysis of Safety

The analysis of safety will focus on AEs with summaries of TEAEs (i.e., AEs that start or increase in severity after the first dose of study treatment). AEs will be coded according to the latest Medical Dictionary for Regulatory Activities (MedDRA) version available at the time of database creation. The severity of AEs will be graded according to NCI CTCAE v5.0.

The number and percent of patients with any AE will be tabulated by system organ class and preferred term using MedDRA. AEs related to danvatirsen, AEs related to pembrolizumab, all SAEs, related SAEs, and AEs by maximum CTCAE grade will be summarized similarly.

Laboratory test results after the first dose of study treatment will be summarized by shift in CTCAE grade for laboratory parameters that can be graded. Laboratory parameters that cannot be graded by CTCAE will be summarized by shifts to low, normal, or high postbaseline.

Vital signs will be summarized by the change from baseline at each postbaseline timepoint. Descriptive statistics will be provided by study visit for physical examination, ECOG performance status, ECG, and weight parameters.

9.7 Analysis of Efficacy

The primary efficacy analysis for ORR, as well as the interim analysis for PFS and OS, will be conducted once all patients are treated and followed for a minimum of 3 months (2 radiologic scans). The final analysis for PFS and OS will be conducted after all patients have been followed for a minimum of 15 months, unless the study is deemed futile at the interim or primary analysis stage.

The overall response will be assessed by the Investigator based on the RECIST v1.1 criteria at each timepoint specified the SoA ([Section 8.1](#)). The best overall response (BOR) will be assessed from response assessments occurring after the first dose of either study treatment up to the first documented assessment of PD that is prior to the initiation of a new anticancer therapy. Objective response (i.e., BOR of PR or CR) will require confirmation of the response (CR or PR) at least 4 weeks after the initial CR or PR.

The ORR will be defined as the proportion of patients with a confirmed objective response as assessed by the Investigator in the FAS. Patients who receive at least one dose of either study treatment but have no valid postbaseline radiographic assessment will be considered non-responders. The ORR will be reported along with the corresponding 2-sided 90% and 95% Clopper-Pearson exact CI. The criteria for promising ORR at the primary analysis are detailed in [Table 9](#) and, in addition, a comparison between the 2 treatment groups will be performed based on Fisher's exact test.

DOR is defined as the date of the patient's first confirmed BOR of CR or PR to the earliest date of documented progression or death if no prior evidence of disease progression, for all patients in the FAS with a confirmed objective response. A patient that starts a new anticancer therapy prior to disease progression will be censored at the date of last valid disease assessment prior to the start of the new anticancer therapy. All other patients without progression or death will be censored at the date of the last valid disease assessment. DOR will be summarized using Kaplan-Meier methods.

The DCR, which includes a BOR of CR, PR, or SD, will be analyzed similar to ORR.

PFS is defined as the time from randomization to the first of either disease progression or death from any cause, where disease progression will be determined based on RECIST v1.1 criteria. A patient that starts a new anticancer therapy prior to disease progression will be censored at the date of last valid disease assessment prior to the start of the new anticancer therapy. Patients without documented disease progression or death will be censored at the last valid disease assessment date. Any patient without a valid disease assessment will be censored on the day of the first dose. PFS will be summarized using Kaplan-Meier methods and compared between the 2 groups using a stratified log rank test.

Sensitivity analyses for ORR, DOR, and PFS will be repeated with the requirement of confirmation of disease progression at least 4 weeks after an initial assessment of PD. Any unconfirmed disease progression assessment will not be counted as PD in these analyses.

OS is defined as the time from randomization to death from any cause. Patients without documentation of death as of the data cutoff will be censored at the last date the patient was known alive. OS will be summarized using Kaplan-Meier methods and compared between the 2 groups using a stratified log rank test.

All efficacy analyses will be performed for two key efficacy subgroups, which includes all patients with CPS ≥ 20 and CPS ≥ 50 . Additional subgroups of interest will be defined in the SAP.

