Study Visit Schedule and Procedures	
The study consists of a screening period, treatment period, safety follow-up, and survival follow-up.
 
After the screening period (Day -28 to Day -1), eligible patients will be randomized in a 2:1 ratio to receive either danvatirsen + pembrolizumab or pembrolizumab monotherapy, respectively. The treatment period consists of sequential 21-day treatment cycles. Patients will receive study treatment until PD, unacceptable toxicity, or voluntary withdrawal.
 
Patients with an initial assessment of PD may remain on treatment until a confirmatory scan is performed at least 4 weeks later to confirm PD prior to removing the patient from study treatment, as long as the progression does not represent a safety risk in the Investigator's judgment.
 
Patients who discontinue study treatment for any reason will have a safety follow-up visit 30 days (+7 days) after the last dose of study treatment and a follow-up for AEs 90 days (+7 days) after the last dose of pembrolizumab.
 
Survival information, including survival status and initiation of new anticancer treatment(s), will be collected every 12 weeks (± 7 days) during the survival follow-up period. The patients may be contacted remotely, and the information collected will be recorded in an electronic case report form.
	
Number of Sites	Approximately 35 sites globally	

Number of Patients	Approximately 81 patients

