Patients in both treatment arms will have radiologic tumor assessments every 6 weeks (± 1 week), regardless of treatment delays, until objective disease progression, initiation of new anticancer treatment, death, withdrawal of consent, or end of study, whichever occurs first.

All patients who discontinue study treatment for any reason will have a safety follow-up visit 30 days (+7 days) after the last dose of study treatment and a follow-up for AEs 90 days (+7 days) after the last dose of pembrolizumab. Patients will be followed for survival at 12-week (± 7 days) intervals until death or withdrawal of consent, whichever occurs first. Survival follow-up will continue until at least 15 months after the last patient is randomized in the study.

The study design is depicted in [Figure 1](#).

Figure 1: Study Scheme

Note: Maximum duration of pembrolizumab treatment is 24 months; there is no limit to the duration of danvatirsen treatment.

Abbreviations: PD = progressive disease; Q3W = every 3 weeks; QW = weekly; SFU = safety follow-up & survival follow-up

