6 DISCONTINUATION AND WITHDRAWAL CRITERIA

6.1 Discontinuation of Study Treatment

After consultation with the medical monitor, patients in the combination arm that are discontinued from one of the study treatments may remain in the study and continue to receive the other study treatment until a discontinuation criterion for the remaining treatment has been met.

Treatment with danvatirsen and pembrolizumab should be permanently discontinued for any of the following:

- Consent withdrawal
- Intolerable AE or an AE that meets the criteria for discontinuation
- Confirmed PD
 - Clinically stable patients who experience radiographic PD by RECIST v1.1 may continue to receive study treatment if patients are otherwise tolerating study treatment in the opinion of the Investigator and there are no signs of rapid, radiographic progression of disease or progression at critical anatomical sites (e.g., cord compression or tumor impinging on a major blood vessel) requiring urgent alternative interventions. Confirmatory imaging should be performed at least 4 weeks later for patients with PD who remain on study treatment. If PD is confirmed, the patient will withdraw from study treatment.
- Clinical progression, in absence of radiographic progression by RECIST v1.1, including intolerable signs or symptoms consistent with disease progression, rapidly worsening laboratory values or relevant tumor markers, rapid decline in ECOG performance status, or impingement of the tumor at critical anatomic sites requiring urgent interventions. Whenever possible, discontinuation due to clinical progression should be discussed with the Medical Monitor
- Pregnancy
- Significant patient non-compliance with the protocol or major protocol deviation
- Investigator decision
- Sponsor decision to end the study.

Patients who discontinue study treatment will complete end-of-treatment (EOT) procedures, safety follow-up, and will enter the survival follow-up phase, as specified in the SoA (Section 8.1). See [Section 7.6](#) for more information.

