7.6.3 Survival Follow-up

All patients who have discontinued the study treatment will continue to be followed for survival information, including survival status and initiation of new anticancer treatment(s). Survival information will be collected every 12 weeks (± 7 days) (telephone communication or in clinic visit) until the study ends. Survival data will be obtained from public records for patients who have been lost to follow-up.

Patients who discontinue study treatment for reasons other than PD will continue to have tumor assessments performed every 6 weeks until PD or the initiation of new anticancer therapy.

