7.7 Imaging Assessments

For all patients, tumor response assessment will be obtained by radiographic imaging with contrast-enhanced CT (preferred) or MRI evaluation. Optimal anatomic coverage for most solid tumors include the chest, abdomen, and pelvis. Coverage should encompass all areas of known predilection for metastases in the disease under evaluation and should additionally investigate areas that may be involved based on signs and symptoms of individual patients. In general, lesions present at baseline should be followed using the same imaging methodology and imaging equipment at subsequent assessments.

Tumor response assessments will be based on evaluation of response of target, non-target, and new lesions according to RECIST v1.1, as detailed in [Appendix 5](#) (all measurements should be recorded in metric notation). Following initial objective response (PR or CR per RECIST v1.1), confirmatory imaging studies should be obtained 4 to 6 weeks later ([Eisenhauer et al 2009](#)).

Before stopping treatment, confirmation of PD should be considered by imaging no less than 4 weeks after initial progression.

The timing of on-study imaging should follow calendar days and **should not** be adjusted for delays in treatment administration or for visits. The same imaging technique should be used in a patient throughout the study for consistency.

For patients who discontinue study treatment for reasons other than PD, radiographic scans should continue according to the respective schedule of assessment until PD, initiation of new anticancer therapy, withdrawal of consent, or at least 15 months after the last patient is

randomized in the study, whichever comes first. Additional imaging may be performed if clinically indicated per the Investigator's discretion.

Brain MRI with or without contrast is the preferred brain imaging modality; however, CT is acceptable if MRI is clinically contraindicated. Patients with treated or untreated parenchymal brain metastases, leptomeningeal disease, or current active malignant epidural disease are excluded from participation in the study (see [Section 4.2](#)). Patients with previously treated epidural disease are allowed as long as disease is inactive. Patients are not required to have brain imaging at screening unless there are suggestive clinical symptoms/suspicion.

During the study, brain CT/MRI scans should be conducted if clinically indicated by development of new specific symptoms.

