- f. To facilitate scheduling of predose assessments, a window of -2 days is allowed to obtain the following procedures prior to dosing a patient: physical examination, weight, laboratory safety tests (hematology, serum chemistry, and coagulation), urinalysis, and thyroid function tests.
- g. Vital signs include temperature, pulse, respiratory rate, blood pressure, and oxygen saturation.
- h. For female patients of childbearing potential, serum or urine. The pregnancy test at the 90 day safety follow up visit is required for all patients in the UK and as clinically indicated for all other patients.
- i. Patients are to be followed up for 30 days (+7 days) after the last dose of study treatment for any new reports of AEs, SAEs, and concomitant medications. Tracking of AEs will continue for all patients treated with pembrolizumab for 90 days (±7 days) after the last dose of pembrolizumab or until the initiation of subsequent anticancer therapy.

Flamingo Therapeutics
Activity and Safety of Danvatirsen and Pembrolizumab in HNSCC
8 May 2025

Trial ID: FLM-6774-201
Amendment 4

- j. Tumor assessments performed within 30 days of C1D1 may be used as the baseline tumor assessments. Tumor assessments will be performed every 6 weeks until tumor progression. Patients who discontinue treatment for reasons other than PD will continue to undergo tumor assessments every 6 weeks until PD or the initiation of new anticancer therapy. To facilitate scheduling of tumor assessments, a window of ± 7 days is allowed.
- k. For C1 Week 1, danvatirsen will be administered on D1, D3, and D5 as a loading dose period. Starting with C1 Week 2, danvatirsen will be administered every week on D1, D8, and D15 of each treatment cycle; doses will have a ± 2 -day dosing window.
- l. For pembrolizumab, a window of ± 7 days is allowed for dosing days. Patients will receive pembrolizumab Q3W on D1 of each cycle.
- m. For C1 Week 1, intense PK sampling will be performed on D1 and D5 for 10 US patients in the danvatirsen + pembrolizumab arm. Sparse PK sampling also occurs on C2D1, C5D1 and EOT for all patients in the danvatirsen + pembrolizumab arm. Detailed PK sampling times are provided in [Table 7](#).
- n. ADA will be assessed for danvatirsen + pembrolizumab patients at C1D1, C2D1, C5D1, and EOT, as shown in [Table 8](#).

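### The protocol's confirmed-progression sensitivity analyses do not count a progression without a confirming scan, yet patients who stop treatment at first progression normally have no such scan scheduled

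*Protocol*

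**What the plan says.** **The analysis rule.** Protocol section 9.7 repeats the ORR, DOR and PFS analyses with the "requirement of confirmation of disease progression at least 4 weeks after an initial assessment of PD". It then says: "Any unconfirmed disease progression assessment will not be counted as PD in these analyses". It has no separate rule for a PD after which no further scan was taken.

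**The scan schedule.**
- Section 3.1 runs 6-weekly scans "until objective disease progression, initiation of new anticancer treatment, death, withdrawal of consent, or end of study, whichever occurs first". Footnote j of the Schedule of Activities (section 8.1) says: "Tumor assessments will be performed every 6 weeks until tumor progression".
- Section 6.1 attaches the confirming scan to continued treatment: "Confirmatory imaging should be performed at least 4 weeks later for patients with PD who remain on study treatment". Continuing is optional. The synopsis says: "Patients with an initial assessment of PD may remain on treatment until a confirmatory scan is performed at least 4 weeks later".
- Section 7.7 is advisory: "Before stopping treatment, confirmation of PD should be considered by imaging no less than 4 weeks after initial progression".
- After treatment ends, scans continue for one group only. Section 7.6.3 says: "Patients who discontinue study treatment for reasons other than PD will continue to have tumor assessments performed every 6 weeks". Section 7.7 and footnote j have the same restriction.

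**The SAP.** Section 5.12.5 plans one sensitivity analysis, which drops the confirmation requirement for response. The output list in section 11 has no table for confirmed progression, and section 9 does not list its removal as a change.

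**The concern.** The rule needs a second scan that the schedule does not provide for patients who stop treatment at first PD. For them, lack of confirmation shows only that nobody looked again, yet the rule treats it like a PD that a later scan overturned.

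The patients affected are not a random subset. Section 6.1 lets clinically stable patients continue and excludes those with rapid progression or progression at critical sites. Those who stop at once, and so lose their PD, will tend to be the faster progressors. The trial is open-label, so willingness to continue and re-scan may also differ by arm. A sensitivity analysis meant to test whether early PD calls matter could then show an arm difference that comes only from who was re-scanned.

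**Working it through.** **Step 1. Who has a scan at least 4 weeks after first PD?**

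| Patient | Scan set by the protocol |
|---|---|
| Stays on treatment after PD | Yes (6.1) |
| Stops at first PD | None after stopping (7.6.3, 7.7, footnote j); beforehand, confirmation is only to be considered (7.7) |
| Stops for another reason | 6-weekly scans continue until PD (7.6.3) |

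The Schedule of Activities also shows a tumor assessment at end of treatment. That visit takes place as soon as possible after stopping (7.6), and footnote a waives imaging done in the previous 30 days. It will not normally supply a scan 4 weeks after the PD scan.

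**Step 2. What happens to a patient who stops at first PD and has no later scan?**
- PFS (9.7): with no counted PD, the patient is censored at the last valid assessment unless a death is documented. If new anticancer therapy starts first, it now precedes any counted progression. The patient is censored before it, and a later death is not an event.
- DOR: a responder is censored in the same way.
- ORR: with no scan after the PD, the patient cannot gain a response, so the distortion falls on PFS and DOR.

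**Step 3. Size.** The plan gives no figure on this point to reproduce, so the inputs below are assumptions, apart from the 6-week interval and the 15-month follow-up, which follow the protocol.
- Exponential PFS with a true median of 3.5 months, scans every 6 weeks (1.38 months) and cutoff at 15 months.
- 15% of first events are deaths.
- A share f of first PDs, chosen at random, is never re-imaged and is censored at that scan.
- Either none or half of these patients later die as a counted event, on average 3 months later.

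If no later death counts, the rule removes 0.85f of events, so the hazard is multiplied by 1 - 0.85f. Then:

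PFS at 6 months (sensitivity) ≈ PFS at 6 months (main)^(1 - 0.85f)

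The simulated main analysis gives 33% at 6 months and a median of 4.14 months (three scan intervals).

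| f | Exponent | Formula | Simulated, no later deaths counted | Simulated, half counted |
|---|---|---|---|---|
| 20% | 0.83 | 0.33^0.83 = 39.8% | 39.9% | 38.7% |
| 40% | 0.66 | 0.33^0.66 = 48.1% | 48.2% | 45.1% |
| 60% | 0.49 | 0.33^0.49 = 58.1% | 58.3% | 51.6% |

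At f = 60% the median is 6.41 to 8.28 months, which is 6.41/4.14 = 1.5 to 8.28/4.14 = 2.0 times the main value. Events per 100 patients fall from 94 to 46-68. With a true median of 5 months, 6-month PFS goes from 46% to 51-53% at f = 20% and to 63-68% at f = 60%.

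**Step 4. Different f by arm, no true effect** (true median 4 months in both arms, ratio of events per person-time, combination to control):

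ratio ≈ (1 - 0.85 × f in combination) / (1 - 0.85 × f in control)

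- 50% combination, 20% control: 0.575/0.83 = 0.69; simulated 0.69, or 0.81 with half the later deaths counted.
- 20% combination, 50% control: 0.83/0.575 = 1.44; simulated 1.44, or 1.24.
- 50% in both arms: 0.99 to 1.00.

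**Step 5. After the fix.** If a PD with no later scan counts on its first date, these patients contribute the same event as in the main analysis. This is the f = 0 case: median 4.14 months, 6-month PFS 33%, ratio 1.0. Any remaining difference from the main analysis then comes from PDs that a later scan overturned.

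**The case against.** The strongest reply is that the reach is small. This is a sensitivity analysis of results that, for DOR and PFS, are secondary, and SAP section 5.12.7 treats secondary and supportive results as descriptive. The SAP does not carry the analysis, so on the current plan no such table would be produced. All of this stands and limits the point. It does not remove it, because the protocol still promises the analysis and no SAP rule closes the gap.

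A second reply is that confirming PD before stopping is the pathway described: section 6.1 lists confirmed PD as a stopping criterion, section 7.7 asks that confirmation be considered, and there is an end-of-treatment scan. A reader might infer from the schedule that a PD in a patient who stops can never be confirmed. That is too strong, since a site may re-scan before stopping, and an end-of-treatment scan may occasionally fall late enough. What stands is that no such scan is required, and normally none is scheduled.

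A reader might also infer that a patient treated beyond an unconfirmed first PD has no scheduled scans at all, because section 3.1 and footnote j end scans at progression. Section 7.5 continues assessments until the section 6.1 criteria are met, and the Schedule of Activities grid shows tumor assessments from Cycle 5 on. The passages are loosely worded against each other and need reconciling; they do not establish that scanning stops.

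Finally, a simple model without deaths multiplies the median by 1/(1 - f), which is 1/0.4 = 2.5 at f = 60%. Counting deaths brings this to 1.5 to 2.0. The true bias could be said to be larger still, because fast progressors are the ones dropped. That was not calculated, and fast progressors who die without new therapy still count as PFS events.

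**Conclusion.** The concern holds for the protocol's confirmed-PD sensitivity analyses only. As written, the rule turns the absence of a scan into the absence of progression, for patients who are likely to be the faster progressors. A reader might take this to threaten the primary ORR decision or the main PFS and DOR results. It does not, because those analyses use first PD.

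The bias grows with f and with any arm difference in f. The documents give neither, so the figures above show a plausible range and are not estimates. They rest on an exponential model, 15% of first events being deaths, f between 0% and 60%, and random selection of the patients not re-imaged. They therefore do not model the informative part. At f = 20% in both arms the effect on 6-month PFS is 6 to 7 points. An arm imbalance of 50% against 20% is enough to create an apparent effect in either direction.

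**What to change.** 1. **Protocol 9.7:** state that a first PD counts as PD on its first date unless a later evaluable scan at least 4 weeks afterwards shows that it is not PD. Absence of a later scan then does not make a PD uncounted.
2. **Reporting:** give by arm the number of first PDs confirmed, overturned and never re-imaged.
3. **SAP:** add the analysis and this rule to section 5.12.5, or record its removal in section 9.
4. **Consistency:** reconcile the scan end-point wording in section 3.1 and footnote j with sections 6.1 and 7.5 for patients treated beyond a first PD. No new scan schedule is proposed. SAP section 9 reports early termination, so the analysis rule now matters more than any change to imaging.

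The cost is a short wording amendment, with whatever approval it needs under section 10.2, and slightly more analysis work. Any SAP change must be approved before database lock (SAP section 5).
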